Södra Älvborgs Hospital, Borås, Sweden

e-mail: [contact]

[name]

Frölunda sjukhus, Västra Frölunda, Sweden

e-mail: [contact]

Summary

Background

Stress related ill health is today a common cause for long term sick leave among women in their midst of life as well as being a common cause for visits to the primary health care.

Aim

To investigate the effect on mental health, quality of life and sick leave of education provided within the primary health care given in group or individually for women aged 45-60 years with stress related symptoms.

Methods

This is a randomised controlled clinical trial using a two factor design.

Education is given as four sessions exploring menopause, physiology, oestrogen deficiency, cardiovascular health, consequences of stress, mental health, relationships, sexuality and lust as well as potential actions to improve the situation. In addition, the group sessions will touch base on topics like obstacles and resources, coping strategies, and behavioural changes.

The individual education will be person-centred and given as five sessions focusing on stress related symptoms, ill health, physiology and coping strategies.

Expected result

If any of these two interventions turns out to be successful it may provide low cost intervention options for a common problem often seen in primary health care.

Study protocol: Effect of primary care education on mental health, quality of life, need for sick leave and health care consumption in women 45-60 years with stress-related symptoms. A randomized controlled trial.

Introduction

Stress-related ill health is today the most common cause of long-term sick leave in women in the middle of life and a common cause of primary care visits (1). It is clear that women suffer from long-term sickness and ill health to a greater degree than men (2). Women's physical and mental health in Sweden shows a marked decrease in the ages of 45-60 years (3). During this life phase, called menopause, the woman undergoes a hormonal transformation (3). Stress-related symptoms appear after a long time with high stress load without sufficient recovery (4). There are currently few studies with high evidence-based treatment on stress-related symptoms (5). Busch et al show in an evaluation that 70% of people who have undergone rehabilitation overall are satisfied with the treatment. The treatment, on the other hand, has not led to increased return to work (6).

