Research shows that women often lack information about physical and mental and urogenital changes under the "middle of life" / menopause (7).

Group education is a method and participation in group education can be a good way for women to get information and exchange experiences (8).

Earlier studies evaluating patient education in hypertension and diabetes show significant improvement (9.10). Talking can raise awareness about choices and consequences, create insight into behaviours and provide insight into the overall life situation to find the core of ill health (11). Arving et al shows that health-related quality of life increased faster in patients receiving support calls than those who received normal treatment (12).

There is a lack of primary care studies that evaluate the effect of education in group and / or individually for women 45-60 years with stress-related symptoms.

The vast number of middle aged women with ill health and subsequent high risk for disease risk and increasing number of long-term sick leave shows that it is important to study women's health in this age group.

Aim

To study the effect of education in a group or individually delivered in primary health care on mental health, quality of life and sick leave in women aged 45-60 with stress-related symptoms.

Research questions

- A. Is there any effect of group information (GI) on quality of life, mental health, sick leave or visits to a primary health care centre compared to a control group?
 1. What is the effect of group education (GI) on quality of life (measured by change in scores in SF36 from baseline to 6 months after completed intervention) –
Primary research question (other questions are secondary).

Study protocol: Effect of primary care education on mental health, quality of life, need for sick leave and health care consumption in women 45-60 years with stress-related symptoms. A randomized controlled trial.

2. What is the effect of group education (GI) on quality of life (measured by change in scores in SF36 from baseline to 12 months after completed intervention)
3. What is the effect of group education (GI) on change in number of days on sick leave. (At baseline the number of days on sick leave up until present time is stated by women currently being on sick leave. At the 6 month follow the same information is retrieved is retrieved. The change is the difference between these measurements.)

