4. What is the effect of group education (GI) on change in number of days on sick leave. (At baseline the number of days on sick leave up until present time is stated by women currently being on sick leave. At the 12 month follow the same information is retrieved is retrieved. The change is the difference between these measurements.)
5. What is the effect of group education (GI) on depressive mood (measured by change in scores in MADRS from baseline to 6 months after completed intervention)
6. What is the effect of group education (GI) on depressive mood (measured by change in scores in MADRS from baseline to 12 months after completed intervention)
7. What is the effect of group education (GI) on stress levels (measured by change in scores in PSS-14 from baseline to 6 months after completed intervention).
8. What is the effect of group education (GI) on stress levels (measured by change in scores in PSS-14 from baseline to 12 months after completed intervention).
9. What is the effect of group education (GI) on stress levels (measured by change in scores in HAD from baseline to 6 months after completed intervention).
10. What is the effect of group education (GI) on stress levels (measured by change in scores in HAD from baseline to 12 months after completed intervention).
11. What is the effect of group education (GI) on visits to primary health care? (women are asked at baseline if they had to visit the primary health care center during the preceding two months. The same question is asked at 6 months. The measurement is the change in proportion of women who visited the primary health care center).
12. What is the effect of group education (GI) on visits to primary health care? (women are asked at baseline if they had to visit the primary health care center during the preceding two months. The same question is asked at 12 months. The measurement is the change in proportion of women who visited the primary health care center).
- B. Is there any effect of structured person-centered support (PCS) on quality of life, mental health, sick leave or visits to a primary health care centre compared to a control group?
13. What is the effect of Structured person-centered support (PCS) on quality of life (measured by change in scores in SF36 from baseline to 6 months after completed intervention)?

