The research nurse is responsible for administration of questionnaires and arranging physical check-up.

Group allocation

Research randomizer is used to generate a random series based on block-randomization in blocks of four. The random series is transferred to closed sealed opaque envelopes, each containing group assignment. The manufacture of these closed envelopes is done by a person who is not involved in the study.

Randomization occurs after the woman answered all questionnaires at baseline. Then the research nurse opens the next sealed numbered envelope and the patch inside describes what group the woman is allocated to:

- Group 1: group information (GI)
- Group 2: group information (GI) + person-centred support (PCS)
- Group 3: person-centred support (PCS)
- Group 4: no GI or PCS (control group)

Intervention

Group information (GI).

Midwives and district nurses participate as group leaders. Each group training includes 12 women and comprises four one-and-a-half hours of information with topics related to physical and mental changes in the body as well as conversations aimed to make behaviour, consequences of behaviour and choices in life conscious.

Study protocol: Effect of primary care education on mental health, quality of life, need for sick leave and health care consumption in women 45-60 years with stress-related symptoms. A randomized controlled trial.

The first group event contains education with the definition and myths of "middle of life" / menopause, physiology, menstrual cycle, hormonal conversion, local oestrogen deficiency symptoms, osteoporosis and information on treatment options and self-care advice.

The second group event contains teaching and information on cardiovascular health, its risk and health factors, physiology, mental health, relationships, sexuality and lust as well as information on treatment options and self-care advice.

The third group event contains insights into stress-related ill health, physiology, social relationships in family and work, sexuality and lust, insight into obstacles and resources, coping strategies and behavioural changes to promote health.

The fourth group event contains insights on relationships, sexuality and lust as well as a summary of "How do we want to live to feel good?" Insight into obstacles and resources, coping strategies and behavioural changes to promote health.

Structured person-centred support (PCS):

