- MADRS: investigates the degree of depression and depressive symptoms. The questionnaire consists of 9 questions, which are graded on a 6-degree scale where 0 points indicate a low incidence of symptoms and 6 points indicate a high incidence of symptoms and ill health. The instrument has been tested for reliability and validity (15).
- SF-36: examines physical and mental health as well as changes over time. The questionnaire consists of 36 multiple-choice questions, divided into eight subdivisions. Scores are between 0 - 100, higher value indicates better health experience. The instrument has been tested for reliability and validity (16).
- HAD: investigates the degree of anxiety and depressive symptoms. The form consists of 14 questions with seven issues that measure anxiety (HAD-A) and seven issues that measure depression (HAD-D) and graded on a 4-degree scale. Each question can yield between 0 and 3 points and summed to give a score scale of 0-21 for respective anxiety and depressive symptoms. Higher points indicate higher incidence of symptoms. The instrument has been tested for reliability and validity (17).
- s-UMS, self-assessed fatigue syndrome. Identify individuals who have developed or may be developing a clinical fatigue syndrome with impaired work ability and increased risk of sick leave. The form has four questions with queries. The instrument has been tested for reliability and validity (18).
- PSS-14: Measurement of self-assessed general perceived stress. how often you have experienced life as unpredictable, uncontrollable and congestive in the last month. The form has fourteen questions. The Swedish translation has shown good internal validity (19).
- AUDIT: self-assessment test for alcohol consumption and consists of ten questions divided into three domains: consumption, addiction and alcohol-related injuries. Results above the cut-off limit 6 points for women and 8 points for men indicate a risky drinking. The instrument has been tested for reliability and validity (20).

Follow-up of intervention takes place six and twelve months after completion of treatment / education. Midwife and district nurse participate in the follow-up. During this visit, follow-up of quality of life, mental health, care needs and sick leave is made by the woman filling in the same questionnaire as at baseline.

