Data is collected by the research nurse at baseline and six and twelve months after completion of education. Returned questionnaires are encoded and code lists will be filed at the R & D unit Södra Älvborg in a locked and fireproof archive for more than ten years. Code key is stored separately. Access to the material has project managers and supervisors. Electronic stored data is stored on the computer's network device H so it is backed up automatically, not on the workstation hard drive. Data is stored on the Västra Götaland region password-protected computer. Tape and video recordings are not used.

Study protocol: Effect of primary care education on mental health, quality of life, need for sick leave and health care consumption in women 45-60 years with stress-related symptoms. A randomized controlled trial.

Statistical analysis

Questionnaires are summarized according to manuals. Data is described descriptively with appropriate estimates. The scientific research questions will be analysed by multivariate regression where the two interventions GI and PCS, each being an independent variable, is entered a two-factor model, where interaction effects between the two interventions is also evaluated. Moreover, age becomes an independent confounding variable. A regression is made for each outcome measure (each scientific question). The level of significance is set to ≤ 0.05 . IBM SPSS version 20 or later will be used.

Sample size estimation

Sample size estimations are made for research questions 1, 3 and 5. When estimating sample size, we assume a significance level of 0.05, power of 0.80 and that we do a two-way test. When estimating sample sizes, we use simple group comparison for two independent groups with Mann-Whitney's test as surrogate test.

Research question	Assumptions	Assumed "Effect size"	Number required
1 (primary)	We assume that the quality of life increases by three points in the intervention group and zero points in the control group. Furthermore, the standard deviation is eight in both groups.	0,38	236
3	We assume that days on sick leave decrease by two days in the intervention group and by 0.5 days in the control group. Furthermore, the standard deviation is five days in both groups.	0.30	368

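### The regressions for SF-36, MADRS, PSS-14 and HAD change scores leave out the baseline score, and the plan does not name the contrast that answers the group-information question

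*Combined protocol and SAP*

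**What the plan says.** **Outcomes.** Primary question 1 is the effect of GI on quality of life, "measured by change in scores in SF36 from baseline to 6 months after completed intervention". The MADRS, PSS-14 and HAD questions are also changes from baseline, at 6 and 12 months. Together with SF-36 and the matching PCS questions they make 16 questions: 1, 2, 5–10, 13, 14 and 17–22.

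**Model.** The Statistical analysis section enters GI and PCS in a two-factor model and also evaluates their interaction. It then adds: "Moreover, age becomes an independent confounding variable. A regression is made for each outcome measure (each scientific question"). No section lists a baseline score as a covariate.

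**Availability of baseline.** Under Group allocation: "Randomization occurs after the woman answered all questionnaires at baseline". Under Data collection, the follow-up assessment "is made by the woman filling in the same questionnaire as at baseline".

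**Contrast.** The Summary states: "This is a randomised controlled clinical trial using a two factor design". Research question A asks for the GI effect relative to a control group, and Group allocation gives that label to Group 4 only (neither GI nor PCS). The sample size section uses a simple comparison of two independent groups. It requires 236, 368 and 312 women for questions 1, 3 and 5 and plans 370.

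**The concern.** **Baseline score.** In a randomised trial, a change score is a baseline adjustment whose coefficient is fixed at 1. Chance imbalance is then corrected by subtraction only, whatever the actual relation between baseline and follow-up. Entering the baseline score lets the data set the coefficient. The plan already accepts covariate adjustment, through age, but omits the outcome's own baseline. At stake is the width of the interval for the primary question and for the other 15 questionnaire questions. Most of those were never sized: only questions 1 and 5 among the 16 have a sample size calculation.

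**Contrast.** Without a sentence naming the GI contrast, two tests fit the text. They use different numbers of women and differ widely in power. If the interaction stays in the model, the coding of the two factors alone decides which test the software's GI coefficient reports. The choice would then be made at analysis.

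**Working it through.** **Inputs from the sample size section.** Two-sided alpha 0.05, power 0.80, 370 women.
- Question 1: 3 points against 0, SD 8, d = 3/8 = 0.375.
- Question 3: decreases of 2 and 0.5 days, SD 5, d = 1.5/5 = 0.30.
- Question 5: −1.5 against +0.10, SDs 5.0 and 4.8. Pooled SD = √[(25 + 23.04)/2] = 4.901; d = 1.6/4.901 = 0.3265.

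**Assumptions not in the documents.** Equal arms (blocks of four over four groups suggest this, but no ratio is stated); the stated SDs are SDs of change; correlation r between baseline and follow-up; k = baseline SD / follow-up SD; a 10% loss, giving 333 women, as a second scenario.

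**1. The plan's own sizes.** A two-sample noncentral t calculation with the Mann-Whitney relative efficiency 3/π gives totals of 236, 368 and 312. All three match the plan. They are totals for two groups.

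**2. Gain from the baseline covariate.** With follow-up variance set to 1, the variance of change is 1 + k² − 2rk. The residual variance after adjusting for baseline is 1 − r². The ratio is

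(1 − r²)/(1 + k² − 2rk) = 1 − (k − r)²/(1 + k² − 2rk).

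It is never above 1, equals (1 + r)/2 at k = 1, and equals 1 at k = r.

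For question 1 with 370 women, the SE of GI against no GI is 8 × √(2/185) = 0.832. At r = 0.5 and k = 1 it becomes 0.832 × √0.75 = 0.720. Results at k = 1:

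| | Change score | r = 0.3 | r = 0.5 | r = 0.7 |
|---|---|---|---|---|
| Variance ratio | 1 | 0.65 | 0.75 | 0.85 |
| Q1 half-width, 370 women | 1.64 | 1.32 | 1.42 | 1.51 |
| Q1 half-width, 333 women | 1.72 | 1.39 | 1.49 | 1.59 |
| Q1 t-based power, 370 women | 0.949 | 0.994 | 0.986 | 0.974 |
| Q5 t-based power, 370 women | 0.879 | 0.973 | 0.951 | 0.925 |
| Q5 t-based power, 333 women | 0.844 | 0.958 | 0.929 | 0.896 |

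Simulating question 5 with four equal arms (GI, PCS and age in the model, no interaction, k = 1) agrees: at 370 women, power is 0.87–0.88 for the change score and 0.97, 0.95 and 0.93 with baseline.

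The gain depends on k. At r = 0.5 the ratio is 0.75, 0.86, 0.95 and 1.00 for k = 1, 0.85, 0.7 and 0.5.

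**3. The two readings of the GI test.** Mann-Whitney power for questions 1 / 3 / 5:

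| | 370 women | 333 women |
|---|---|---|
| GI v no GI, all women | 0.94 / 0.80 / 0.86 | 0.92 / 0.76 / 0.83 |
| Group 1 v Group 4 | 0.70 / 0.51 / 0.58 | 0.65 / 0.47 / 0.53 |

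At 370 women the gap is 0.24 to 0.29. Question 3 passes 0.80 only under the first reading, and only while at least 368 women are analysed (0.8007 at 368, 0.7997 at 367).

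**4. How the second reading can arise from the model.** With 0/1 coding and the interaction kept, the GI coefficient is Group 1 minus Group 4. Simulating question 1 without baseline gave it a power of about 0.72. Centred coding of the same model returned the pooled effect, with power 0.95 to 0.96. The mean estimate was about 3.0 in every model, which confirms that the issue is precision and not bias.

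**The case against.** **The change-score analysis is legitimate.** It is pre-specified, unbiased and already uses the baseline data. On the pooled contrast, question 1 has power of about 0.95 before any adjustment. This stands: the primary test is not short of power on that reading, and the benefit there is mainly a narrower interval.

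**The size of the gain is assumed.** The documents give neither r nor k. The inclusion criteria require some health problem and exclude severe depression, which could narrow the baseline spread and put k below 1. At r = 0.7 and k = 0.85 the variance falls by only 4%: the question 1 half-width goes from 1.64 to 1.60 and question 5 power from 0.88 to 0.89. This stands too. But the ratio cannot exceed 1, so the most the sponsor gives up is one degree of freedom per model.

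**The contrast can be inferred.** The two-factor design, the two-group sizes and 370 planned against 368 required all favour GI against no GI. That is the likelier reading, but question A and the Group 4 label point the other way, and the analysis section does not settle it.

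**Dropping the interaction is not the only remedy.** Centred coding with the interaction kept gives the pooled effect at essentially no loss of power. That is correct, and it would be acceptable if stated in advance.

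**Question 3 is idealised.** The power above lets every woman contribute, while the plan says: "At baseline the number of days on sick leave up until present time is stated by women currently being on sick leave". The question 3 figures therefore take the plan's own sizing at face value.

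**Conclusion.** The concern holds, as a recommended improvement and not as a flaw that invalidates the trial. The baseline score is absent from the model although it is measured before randomisation. Adding it cuts the variance by 15% to 35% for r between 0.7 and 0.3 with equal SDs, by less when k lies closer to r, and by nothing at k = r. That the score is omitted is certain; how much precision is lost is conditional on r and k.

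The unnamed contrast needs no assumption about r or k. With equal arms and the plan's own effects, the Group 1 v Group 4 reading leaves all three sized questions below the planned 0.80.

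The covariate point covers the four questionnaire scores only. It does not extend to sick-leave days, where baseline days come from women then on sick leave, or to visits, where "The measurement is the change in proportion of women who visited the primary health care center".

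**What to change.** 1. **Add the baseline value of the same score** as a covariate in the regressions for questions 1, 2, 5–10, 13, 14 and 17–22. For SF-36, first name the score that question 1 uses: "The questionnaire consists of 36 multiple-choice questions, divided into eight subdivisions", and the question names none of them. The covariate is the baseline of that score. For HAD, use each subscale's own baseline. Leave the sick-leave and visit questions unchanged under this fix.

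2. **Name the contrast.** State that the primary GI and PCS tests are main effects from a model with GI, PCS, age and, for the scores, baseline, without the interaction. Test the interaction in a separate secondary model, report the four cell means, and reword questions A and B to match.

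**Cost.** No new data are needed. Item 1 takes one degree of freedom per model and one sentence naming the SF-36 score. Item 2 takes a rewording of questions A and B, and has a real downside: the main effect averages over the other intervention. As an assumed example for question 1, if GI gives 3 points without PCS and 1.5 with it, the main effect is (3 + 1.5)/2 = 2.25 points and Mann-Whitney power with 370 women falls from 0.94 to 0.75. If GI gives nothing with PCS, the main effect is 1.5 points and power is 0.42. The cell means must therefore be read beside the main effect.
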